15.4 Analysis of Secondary Endpoints

Categorical variables will be summarized as frequency and percentage, and continuous variables as median and interquartile range by arm. Categorical variables will be compared between the two arms by either chi-square or Fisher's exact test, as appropriate.³⁹ Continuous variables will be compared between the two arms by two-sample t-tests, or Mann-Whitney U tests if the normality assumption does not hold. Logistic regression (simple and multiple) will be used to detect variables associated with presence or absence of AKI. Patient and graft survival and time-to-event data (such as time to disease progression) will be estimated by Kaplan-Meier method and compared between the two arms by log-rank tests and cox-proportional hazard model will be applied to facilitate incorporating other covariates in the model. Statistical analysis will be performed using GraphPad Prism, STATA, and R software.

- To check if the frequencies of categories of AKI (Stage 1, 2, or 3 or no AKI) are different between the two arms, a chi-square test will be used. Similarly, a multiple proportional odds model will be applied when considering AKI in a multi-category fashion.
- Duration of intensive care unit stay and hospital stay will be summarized by median and interquartile range by arm and compared by two-sample t-tests, or Mann-Whitney U tests if the normality assumption does not hold.

- Patient survival will be estimated by the Kaplan-Meier method and compared between the two arms by log-rank tests. A Cox-proportional hazard model will be applied to facilitate incorporating other covariates into the model.
- Incidence of post-operative renal replacement therapy within 7-days, at 30-days, and at 1 year after transplant will be summarized as frequency and percentage, and compared between the two arms by either chi-square or Fisher's exact test, as appropriate.
- Incidence of persistent renal dysfunction (defined as a reduction in glomerular filtration rate by ≥ 25 mL/min or ≥ 50% from baseline) at 90-days and 1-year after transplant will be summarized as frequency and percentage, and compared between the two arms by either chi-square or Fisher's exact test, as appropriate.
- The change in serum NGAL level from baseline to 2 hours after reperfusion of the portal vein will be summarized by median and interquartile range by arm and compared by two-sample t-tests, or Mann-Whitney U tests if the normality assumption does not hold.
- The change in urine NGAL level from baseline to 2 hours after reperfusion of the portal vein will be summarized by median and interquartile range by arm and compared by two-sample t-tests, or Mann-Whitney U tests if the normality assumption does not hold.

Safety and tolerability data will be summarized by treatment group.

Adverse event rates will be coded by body system and MedDra classification term. Adverse events will be tabulated by treatment group and will include the number of patients for whom the event occurred, the rate of occurrence, and the severity and relationship to study treatment.

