8.2 Blinding

Due to the objectives of the study, the identity of test and control treatments will not be known to patients. The following study procedures will be in place to ensure single-blind administration of study treatments.

Access to the randomization code will be strictly controlled. The randomization code will not be revealed until the patient has entered the operating room for liver transplantation. The study protocol will be completed in its entirety while the patient is in the operating room under general anesthesia. Therefore, it will be impossible for the patient to know the treatment assignment until the protocol is complete.

No attempt will be made to blind the study doctors (anesthesiologists), who are investigators in the study, to the treatment assignment, as they will be the ones administering and monitoring the temperature protocol during LTx.

Research staff assigned to adjudicate the Primary Outcome (presence or absence of AKI within 72 h of LTx) will be blinded to the treatment assignment and the intraoperative anesthesia record showing the patient's core temperature. Only the preoperative and postoperative values of sCr will be necessary to adjudicate the Primary Outcome.

The study blind will be broken on completion of the clinical study and after the study database has been locked.

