8.3 Formulation of Test and Control Treatments

After induction of general anesthesia, the ECD will be connected to the Gaymar Medi-Therm III Hyper/Hypothermia Machine and tested for leaks according to the manufacturer's instructions. Then, it will be lubricated and placed into the esophagus of the subject in a manner identical to that of the standard OG tube used in LTx surgery.

The standard bladder temperature probe used in LTx operations will be connected to the PATIENT PROBE jack of the Gaymar Medi-Therm III, which will be used in AUTO/Rapid mode.

In both Study Arms (Mild Hypothermia and Normothermia), the subject will be given 2 grams of magnesium (Mg) sulfate IV at the beginning of surgery if the preoperative Mg < 2 mg/dL. This will be done because mild hypothermia may trigger a cold-induced diuresis and loss of electrolytes. Therefore, efforts will be made to keep the Mg normal (1.8-2.4 mg/dL) in both groups. Potassium will also be monitored carefully during surgery and replaced at the discretion of the attending anesthesiologist/study doctor.

Experimental treatment – Mild hypothermia (34-35 °C).

- Cooling will be initiated after induction of anesthesia and maintained throughout the anhepatic phase of LTx (Fig. 1). This will be done by selecting a Set Point temperature of 34.8 °C¹ on the Gaymar Medi-Therm III.
- In all feasible cases the surgeon will cover the peritoneal surface over the right kidney, which is exposed during the operation, with ice-cold sponges (lap sponges soaked in ice water and wrapped around ice cubes) to enhance cooling of the renal parenchyma. Local cooling will be applied to the right kidney beginning approximately 10 minutes prior to the anhepatic phase. The anhepatic phase is defined as application of the inferior vena cava (IVC) clamp and removal of the recipient liver.
- After the portal vein is reperfused, the ECD (by selecting a Set Point temperature of 37 °C on the Gaymar Medi-Therm III) and other standard measures (forced-air, fluid, and table warmers, plus a heated anesthesia circuit) will be used to actively re-warm the patient (expected warming rate ≥ 1 °C/hour). The goal is to achieve normothermia by case end.

Control – Normothermia (36.5-37.5 °C).

• After induction of anesthesia, the ECD (by selecting a Set Point temperature of 37 °C on the Gaymar Medi-Therm III) and standard warming measures will be used to maintain normothermia throughout the operation.

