9.3 Research Laboratory Measurements

9.3.1 Serum NGAL Measurements

At two time points, baseline (surgical incision) and 2 hours after reperfusion of the portal vein, blood will be collected for serum NGAL determination. At each blood draw, two serum separator tubes (gold top) will be filled. Each tube requires about 5 mL of blood, there will be 2 tubes collected per time point, and 2 time points, for a total of about 20 mL of blood (4 tubes).

After filling with blood, tubes will be inverted 5-times to mix clot activator with blood. Samples will sit undisturbed for 30 min to allow clot to form. Samples will be centrifuged at 1,000 x g for 15 minutes. Serum will be pipetted into Eppendorf tubes in 2 mL aliquots and frozen at \leq -20 °C until analysis, which will be performed *en batch*.

Serum NGAL determination will be performed using an enzyme-linked immunosorbent assay (ELISA) kit according to the manufacturer's instructions (R&D Systems, Inc.).

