9.3.2 Urine NGAL Measurements

At two time points, baseline (surgical incision) and 2 hours after reperfusion of the portal vein, urine will be collected for NGAL determination. Approximately 10-15 mL of fresh urine will be aspirated from the Foley catheter collection chamber using a syringe, and dispensed into a 15-mL sterile tube (Falcon). The urine will be centrifuged at 1,000 x g for 15 min to pellet any solid material. The supernatant will be pipetted into Eppendorf tubes in 2 mL aliquots and frozen at \leq -20 °C until analysis, which will be performed *en batch*.

Urine NGAL determination will be performed using an ELISA kit according to the manufacturer's instructions (R&D Systems, Inc.).

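### The NGAL comparisons leave the baseline value unused as a covariate, and the urine comparison has no pre-specified handling of dilution

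*Combined protocol and SAP*

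**What the plan says.** - **Tests.** Section 15.4 plans to compare "The change in serum NGAL level from baseline to 2 hours after reperfusion of the portal vein" and "The change in urine NGAL level from baseline to 2 hours after reperfusion of the portal vein", each "compared by two-sample t-tests, or Mann-Whitney U tests if the normality assumption does not hold". The covariate models in Sections 15.3 and 15.4 (logistic, proportional odds, Cox) are for AKI and time-to-event outcomes; none is set for NGAL.
- **Sampling.** Section 9.3.2: "At two time points, baseline (surgical incision) and 2 hours after reperfusion of the portal vein, urine will be collected for NGAL determination". Section 9.3.1 sets the same times for serum. Urine is drawn from the Foley collection chamber and assayed for NGAL only. No urine creatinine, timed volume or other dilution correction is specified.
- **Treatment timing.** Section 8.3: "Cooling will be initiated after induction of anesthesia and maintained throughout the anhepatic phase of LTx". Section 8.2: "The randomization code will not be revealed until the patient has entered the operating room for liver transplantation". Section 10.1 lists the temperature protocol before the NGAL collections.
- **Diuresis.** In explaining why magnesium is managed in both arms, Section 8.3 says that "mild hypothermia may trigger a cold-induced diuresis and loss of electrolytes".
- **Urine output.** Section 5.4 tallies it at operative milestones from incision to skin closure. Two hours after reperfusion is not one of them, and the tallies are not linked to NGAL.
- **Later SAP.** Section 15 promises a detailed SAP before the final data are analysed.

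**The concern.** Reducing early AKI biomarkers is a named secondary objective in the Synopsis. Two things weaken what the NGAL results can show.

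First, the baseline enters only by subtraction, which usually uses it less efficiently than a regression that estimates its weight.

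Second, a urine concentration falls when urine flow rises, even if the kidney excretes the same amount of NGAL. If cooling raises flow, lower urine NGAL in the cooled arm could mean less injury, more dilution, or both, and the plan has no rule for telling them apart. Serum NGAL helps only in part, because Section 3.2 ties the two markers to different kinds of injury.

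The baseline sample complicates both matters. If cooling has begun by incision, dilution may be present in both urine samples, which can shrink or reverse the bias in the change.

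**Working it through.** **1. The plan's own figure.** The documents state nothing numerical for NGAL. The only design figure is 101 per arm for AKI (Section 15.6). With 68% against 0.68 × 0.7 = 47.6%, two-sided 0.05 and 80% power, the two-proportion formula gives 91, or 101 with continuity correction. It reproduces, but it concerns AKI. It serves here only as the number of patients per arm.

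**2. Assumed inputs.** Log NGAL bivariate normal; 3-fold rise; correlation ρ between the two times of 0.3, 0.5 or 0.7; log SD 1.0 at both times unless stated; change taken on the raw scale; two-sided 5%. Mann-Whitney figures are simulated; the regression figures follow from the formulas below.

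**3. Power, true ratio 0.7.** For log(2-hour) regressed on arm and log(baseline), SE = s₂ × √(1 − ρ²) × √(2/101), and power ≈ Φ(|ln 0.7|/SE − 1.96), with |ln 0.7| = 0.357. Example at ρ = 0.5 and s₂ = 1: SE = 0.866 × 0.1407 = 0.1219, and Φ(2.93 − 1.96) = 83%.

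| Log SD (baseline, 2 h) | Mann-Whitney on raw change, ρ 0.3/0.5/0.7 | Log-adjusted |
|---|---|---|
| 1.0, 1.0 | 66/76/90% | 75/83/94% |
| 0.6, 1.2 | 56/61/67% | 60/68/84% |

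The gain is 4–17 points in this table and about 3–17 once simulation error is allowed for. log(2-hour) on arm alone has Φ(0.357/0.1407 − 1.96) = 72% power at log SD 1.0.

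Against a change-score t-test, the variance ratio is k²(1 − ρ²)/(1 + k² − 2kρ), where k is the ratio of the 2-hour SD to the baseline SD. At k = 1 it is 0.65/0.75/0.85, so a test with 60% power rises to 78/72/67%. At k = 1.5 the adjusted power is 66/62/60%, and at k = 2 it is 62/60/63%. This 60–78% range applies only if the t-test is used.

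**4. False positives on raw urine NGAL, equal true excretion.** Let r₀ and r₂ be the dilution ratios of the cooled arm at incision and at 2 hours. The adjusted estimate shifts by D = ln r₂ − ρ ln r₀, with SE = √(1 − ρ²) × 0.1407. The rejection rate is Φ(|D|/SE − 1.96) + Φ(−|D|/SE − 1.96). For log(2-hour) alone, D = ln r₂ and SE = 0.1407.

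| r₀, r₂ | Planned Mann-Whitney | Log-adjusted, ρ 0.3/0.5/0.7 | log(2-hour) alone |
|---|---|---|---|
| 1, 1 | 5% | 5% | 5% |
| 1, 1.1 | 9–13% | 11/12/16% | 10% |
| 1, 1.25 | 31–51% | 38/45/60% | 35% |
| 1.25, 1.25 | 13–19% | 21/15/10% | 35% |
| 1.25, 1 | 10–13% | 8/15/34% | 5% |
| 1.25, 1.1 | about 5% | 6/5/9% | 10% |

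Rows 2 to 4 err towards hypothermia and row 5 towards control. Example for row 5 at ρ = 0.7: |D| = 0.7 × 0.223 = 0.156, SE = 0.1005, and Φ(1.55 − 1.96) = 34%. Simulation puts this cell at 33–35%.

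**5. Creatinine-normalised urine NGAL.** Dilution cancels in the ratio, so the rate is 5% if creatinine excretion is equal by arm. If excretion is 10% lower in controls at 2 hours, with creatinine noise of log SD 0.3 at each time, the log-ratio regression has 11–16% false positives over the same ρ.

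**The case against.** **The planned test is valid.** This stands. A reader might infer that leaving out the baseline covariate biases the comparison. Under randomisation it does not, provided the incision sample is unaffected by cooling; the cost is precision.

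**The dilution ratios are conjecture.** This stands too. Section 8.3 says only that a diuresis may occur. Sections 4.1 and 8.3 expect rewarming at 1 °C per hour or more, so the 2-hour ratio may be close to 1. At 1.1 the planned test's error (9–13%) is no worse than that of the creatinine index under the unfavourable assumption in step 5. The 31–51% is a scenario, not an estimate. What remains is that the protocol itself names a mechanism and gives no rule for it.

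**The baseline may be clean.** A reader might infer that the baseline is certainly contaminated. The documents support only a probable order: cooling follows induction and sampling is at incision. No interval is stated, the figure is not shown, and Section 10.1 is a task list. Urine in the chamber may partly predate cooling.

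**Adjustment is no cure for urine.** Correct, and it limits the remedy. Baseline adjustment of raw urine NGAL does worse than the planned test in several rows of step 4, and log(2-hour) alone is unprotected when both samples are diluted.

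**The SAP may settle this.** It may. That makes it the natural place for the change.

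**Conclusion.** The point holds as a modest one. For both markers the collected baseline is under-used, at a cost of about 3–17 points of power against Mann-Whitney under the stated assumptions. For urine, dilution has no pre-specified handling although the protocol says cooling may cause a diuresis. The resulting error runs from none (ratio 1) to substantial, and the documents do not say where in that range the trial lies. Every NGAL SD, correlation, rise, effect and flow ratio used here is assumed.

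The documents do not support reading this as evidence that a urine NGAL benefit would be false, or as a threat to the main result. The AKI comparison and the sample size are untouched.

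A separate matter: the start of rewarming is worded differently in the Synopsis, Section 1 and Section 3.2 (flow fully restored to the liver) than in Section 4.1 (15 minutes after portal reperfusion). Those passages must be reconciled.

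**What to change.** Write the following into the SAP before unblinding.

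1. **Serum NGAL.** Make regression of log(2-hour) on arm and log(baseline) the main analysis, and report the ratio of geometric means with 95% CI. Keep the planned change test as supportive and report baseline NGAL by arm. Add log(2-hour) on arm alone as a sensitivity analysis, reported whatever the baseline comparison shows. State that the baseline probably follows the start of cooling. Cost: SAP text and a few extra results. Downside: the model conditions on a value that cooling may already have moved.

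2. **Urine NGAL.** Keep the planned raw-change test, and do not make adjusted raw concentration the main model. Add one analysis that corrects both samples for dilution. The better route is urine creatinine on stored aliquots (10–15 mL in 2 mL aliquots, so about 5 to 7 per time point), analysed as the log NGAL-to-creatinine ratio. The route without an assay uses the Section 5.4 urine output. It is approximate, because no tally is set at 2 hours and none precedes incision. State that log(2-hour) alone does not protect raw urine NGAL against dilution, and that baseline adjustment of raw urine can be worse than the planned test (up to about 35% against 13% false positives if only the incision sample is diluted). Downside: creatinine excretion may itself differ by arm (step 5).

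3. **Disagreement rule.** Report an estimate with 95% CI for both urine analyses. Define disagreement in advance, for example: the raw CI excludes no difference while the corrected CI does not, or the estimates have opposite signs. In that case, claim no kidney protection from urine NGAL.

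Visits, samples, sample size and the primary test do not change.

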15.5 Interim Analysis

15.5.1. Interim Analysis for Efficacy

A single interim analysis for efficacy is planned for this study after 50% of the required patients (101 of the estimated 202) are accrued after accounting for withdrawn subjects. Based on the O'Brien-Fleming approach to calculate alpha spending, during the interim analysis step, if the *p* value is < 0.0054, the study will be stopped as the desired efficacy will have been achieved; if not, then we will continue the study. If the final *p* value is < 0.0492, then we will declare that the AKI status is different between the two arms.

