	sponges to enhance cooling of the renal parenchyma during the	
	anhepatic phase of the operation.	
CONTROL	Normothermia (36.5-37.5 °C) during liver transplantation	
TREATMENT AND	romotiona (50.5 57.5 °C) during irver dunsplanation	
METHOD OF	Normothermia will be maintained using an ECD as well as standard	
ADMINISTRATION	measures after the induction of general anesthesia and throughout the	
	liver transplant operation.	
	Subjects will be on study for up to one year.	
DURATION OF	Screening: less than 1 day	
SUBJECT PARTICIPATION	Treatment: less than 1 day (during liver transplantation)	
	Follow-up: 1 year	
AND DURATION OF	The total duration of the study is expected to be 36 months. 24	
STUDY	months for subject recruitment and 12 for final subject follow-up.	
CONCOMMITANT	Allowed: N/A	
MEDICATIONS	Allowed. N/A	
MEDICATIONS	Prohibited: N/A	
FEELCACY		
EFFICACY EVALUATIONS		
PRIMARY ENDPOINT	Incidence of acute kidney injury within 72 hours after liver	
TRIMARI ENDI OINT	transplantation	
SECONDARY	 Distribution of the stages of acute kidney injury within 72 hours 	
ENDPOINTS	after liver transplantation	
	 Duration of intensive care unit stay 	
	 Duration of hospital stay 	
	 One-year survival rate 	
	 Need for renal replacement therapy within 7-days, at 30-days, and 	
	at 1 year after transplant	
	 Persistent renal dysfunction at 90-days and 1-year after transplant 	
	 Change in serum NGAL levels from baseline to 2 hours after 	
	reperfusion of the portal vein	
	 Change in urine NGAL levels from baseline to 2 hours after 	
	reperfusion of the portal vein	
OTHER	Percentage of intraoperative time within target temperature range	
EVALUATIONS	i i oreentage of intraoperative time within target temperature range	
LIALUAIIUNS	 	

SAFETY EVALUATIONS	 Time to reach normothermia upon initiation of re-warming (mild hypothermia arm) Number of units of blood products transfused (packed red blood cells, fresh frozen plasma, platelets, and cryoprecipitate) Incidence of surgical site infections within 2 weeks of LTx Intraoperative vasopressor doses
PLANNED INTERIM ANALYSES	When 50% of patients have completed the study, an interim analysis for efficacy will be conducted by an independent data safety monitoring board (DSMB).

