4 STUDY DESIGN

4.1 Study Overview

This is a multi-center, single-blind, RCT. 230 subjects are planned. Each subject will have an ECD placed after induction of general anesthesia and undergo LTx with one of two temperature management protocols (Fig. 1). Each subject will receive only one of the two experimental treatments. Subjects will be randomizaed to one of the two treatments. Evaluations will be taken at baseline, and at several intraoperative time points. Data from the electronic medical record will be analyzed post-operatively.

Screening data will be reviewed to determine subject eligibility. Subjects who meet all inclusion criteria and none of the exclusion criteria will be entered into the study.

The following treatment regimens will be used (Fig. 1):

- Experimental treatment Mild hypothermia (34-35 °C). Cooling will be initiated after induction of anesthesia and maintained throughout the anhepatic phase of LTx (Fig. 1). In all feasible cases the surgeon will cover the peritoneal surface over the right kidney, which is exposed during the operation, with ice-cold sponges to enhance cooling of the renal parenchyma. Shortly (15 minutes) after the portal vein is reperfused, the ECD and other standard measures (forced-air, fluid, and table warmers, plus a heated anesthesia circuit) will be used to actively rewarm the patient (expected warming rate ≥ 1 °C/hour). The goal is to achieve normothermia by case end.
- **Control** Normothermia (36.5-37.5 °C). After induction of anesthesia, the ECD and standard warming measures will be used to maintain normothermia throughout the operation.

Total duration of subject participation will be approximately 6-10 hours, which is the duration of surgery. Subjects will be followed up remotely via the electronic medical record (EMR) for 1 year after LTx.

[figure not shown]

Figure 1. Scheme of overall study design showing temperature management protocols.

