13 PROTOCOL VIOLATIONS

A protocol violation occurs when the subject or investigator fails to adhere to significant protocol requirements affecting the inclusion, exclusion, subject safety and primary endpoint criteria. Protocol violations for this study include, but are not limited to, the following:

- Early termination of temperature management protocol
- Removal of ECD prior to the end of surgery
- Failure to pack the right kidney with ice
- Inability to maintain target temperature for ≥ 1 hour
- Failure to meet inclusion/exclusion criteria
- Failure to comply with Good Clinical Practice (GCP) guidelines will also result in a protocol violation.

Protocol violations will be accounted for by intention-to-treat analysis. Withdrawal of the subject will not be required, as all study procedures are completed within the first visit at the time of LTx.

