15.6 Sample Size and Randomization

Considering one interim analysis for efficacy, and given the incidence of AKI in LTx patients at UCSF (68%), we estimate a sample size of 101 subjects per arm (n = 202 total) is needed to detect a 30% reduction in AKI with 80% power at overall alpha = 0.05 (two-tailed).

We will aim to enroll 230 total subjects to allow for just over a 10% drop-out rate, since some subjects may not be able to complete the protocol and will be withdrawn from the study. UCSF is a high-volume center for LTx (> 180 cases per year), the majority of which meet our inclusion criteria. Thus, we estimate it will take no more than two years to complete study enrollment. The website http://www.swogstat.org was used to perform the power calculation, and the power calculation was confirmed by the CTSI at UCSF.

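### Minor: the stopping thresholds 0.0054 and 0.0492 give an overall two-sided alpha of about 0.0513, not 0.05, and the interim trigger is worded in two ways

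*Combined protocol and SAP*

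**What the plan says.** Section 15.5.1 plans a single efficacy analysis once "50% of the required patients (101 of the estimated 202) are accrued after accounting for withdrawn subjects". It cites the O'Brien-Fleming approach to alpha spending. If the interim p "value is < 0.0054, the study will be stopped as the desired efficacy will have been achieved"; otherwise the trial continues, and if the final p "value is < 0.0492, then we will declare that the AKI status is different between the two arms". Section 15.6 and the synopsis state an overall two-tailed alpha of 0.05.

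The synopsis words the timing differently: "When 50% of patients have completed the study, an interim analysis for efficacy will be conducted". It also says "Subjects will be on study for up to one year". Section 4.1, on the other hand, says "Total duration of subject participation will be approximately 6-10 hours, which is the duration of surgery", with remote record follow-up for a year, and Section 13 says "all study procedures are completed within the first visit at the time of LTx". The primary endpoint (Section 5.1) is AKI within 72 hours; neither description of the trigger mentions it.

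**The concern.** The two thresholds are the trial's success rule, and together they are meant to hold the overall error rate at 0.05. An O'Brien-Fleming interim value near 0.0054 at half the information normally goes with a final value near 0.048. A final value near 0.049 goes with an interim value near 0.003. The plan appears to take the interim value from one scheme and a more lenient final value from another. A final p between about 0.048 and 0.0492 would then be called significant although the claimed level is not held.

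The trigger matters for a different reason. If completing the study means one year of follow-up, the look comes close to the end of recruitment and stopping early spares few or no patients, even though the primary outcome is known at 72 hours.

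**Working it through.** **Inputs.** Look at 101/202, so t = 0.50; thresholds 0.0054 and 0.0492 (Section 15.5.1). Overall two-sided alpha 0.05, 80% power, 101 per arm, control AKI rate 68%, 30% reduction read as relative, so 68% v 47.6% (Section 15.6). Test: two-sample proportion test, continuity correction not specified (Section 15.3).

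**Step 1: the plan's sample size.** With mean rate 0.578 and difference 0.204, the uncorrected formula gives n = [1.960 × √(2 × 0.578 × 0.422) + 0.842 × √(0.68 × 0.32 + 0.476 × 0.524)]² / 0.204² = 90.8, or 91 per arm. The continuity-corrected form, (n/4)[1 + √(1 + 4/(n × 0.204))]², gives 100.4, or 101. The stated 101 is reproduced, with the correction.

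**Step 2: overall alpha.** Alpha = 1 − P(|Z1| < c1, |Z2| < c2), with Z1 and Z2 standard normal and correlation √t. Here c1 = z(1 − 0.0054/2) = 2.782 and c2 = z(1 − 0.0492/2) = 1.967.

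- t = 0.50: 0.0513 (0.05129 by integration, 0.05132 in 20 million simulated pairs).
- t = 101/207, if 90% of 230 are analysed: 0.0514.
- Alpha equals 0.0500 at t = 0.70.

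The stated 0.05 is not reproduced.

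**Step 3: O'Brien-Fleming versions at t = 0.50.**

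| Version | Interim p | Final p |
|---|---|---|
| Stated in the plan | 0.0054 | 0.0492 |
| Classical (c = 1.9774; interim bound c√2) | 0.0052 | 0.0480 |
| Spending function, 0.025 per side | 0.0031 | 0.0490 |
| Spending function, two-sided 0.05 | 0.0056 | 0.0478 |

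The spending function is α(t) = 2[1 − Φ(z(1 − α/2)/√t)]. Keeping 0.0054 requires a final threshold of about 0.0479 (0.04787). Keeping 0.0492 requires an interim threshold of about 0.0026.

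**Step 4: exact size.** Enumeration of the pooled test on binomial counts, 51/50 at the look and 101/101 at the end, with the same AKI rate in both arms:

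| Pair | Normal approximation | Exact at 0.68, uncorrected | Exact over 0.45 to 0.75, uncorrected | Exact at 0.68, corrected |
|---|---|---|---|---|
| 0.0054/0.0492 | 0.0513 | 0.0515 | 0.0510 to 0.0590 | 0.0345 |
| 0.0051/0.0480 | 0.0500 | 0.0491 | 0.0472 to 0.0538 | 0.0343 |
| 0.0054/0.0478 | 0.0499 | 0.0495 | up to 0.0532 | 0.0344 |
| 0.0030/0.0490 | 0.0500 | 0.0503 | 0.0498 to 0.0580 | 0.0339 |

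The last pair barely moves the exact size because, at 101 v 101, no attainable uncorrected p lies between 0.0490 and 0.0492.

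**Step 5: power at 68% v 47.6%.** Under the normal approximation, with drift 0.204/√(2 × 0.578 × 0.422/101) = 2.935, power is 83.5% for the stated pair, 83.3% for 0.0051/0.0480, 83.2% for 0.0054/0.0478 and 83.4% for 0.0030/0.0490. By exact enumeration the loss is 0.07 to 0.66 points uncorrected and 0.05 to 0.61 corrected.

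**Step 6: timing.** Assume uniform accrual of 230 over the planned 24 months, or 230/24 = 9.58 per month. Then 101 patients are enrolled at month 10.5 and 115 (half of 230) at month 12. On the one-year reading the look moves to month 22.5, with 22.5 × 9.58 ≈ 216 enrolled and 14 to come, or to month 24 with none to come.

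**The case against.** The strongest objection concerns the form of the test. The 101 per arm matches a continuity-corrected calculation, the only hint in the document about which form was intended. With a corrected test the stated pair has exact size 0.0344 to 0.0420 over common rates 0.45 to 0.75, so the trial would be conservative and a stricter threshold would only cost power. That is fair, but a corrected sample-size formula does not bind the analysis, and Section 15.3 does not specify the correction. Without it the stated pair exceeds 0.05 at every rate examined.

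Binomial discreteness is as large as the defect: the matched pairs also exceed 0.05 at some rates. This stands, and it limits the importance of the point. It does not explain the mismatch, since standard pairs rounded to four decimals hold the nominal level.

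Section 15 promises a SAP that may modify the analysis. It can correct the final threshold, but it is due only before the final analysis, so it need not exist at the interim look.

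On the trigger, Section 15.5.1 gives an explicit count, and Sections 4.1 and 13 support reading completion as the end of the operating-room protocol, under which the two triggers nearly coincide. The one-year reading nevertheless follows from the synopsis itself.

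**Conclusion.** The concern holds and is minor. Under the normal approximation at 50% information the pair spends 0.0513, an excess of 0.0013 over the stated 0.05, and it matches none of the three O'Brien-Fleming versions computed. It changes the conclusion only if the final p falls between the corrected threshold (0.0478 to 0.0490, depending on the pair chosen) and 0.0492, or if a lower interim threshold is adopted and the interim p falls between it and 0.0054. With a continuity-corrected test the actual error rate would be below 0.05 in any case.

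The trigger wording is a genuine inconsistency. Its consequence depends on the one-year reading and on the uniform accrual assumed above.

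**What to change.** Before the interim look, replace the pair in Section 15.5.1 with one that gives 0.05 at 50% information:

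- 0.0051/0.0480 (classical O'Brien-Fleming, interim rounded down from 0.00517); or
- 0.0054/0.0478, which keeps the stated interim value.

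A pair from the spending function, 0.0030/0.0490 with the final threshold recomputed from the actual information fraction, is also valid under the normal approximation, but it hardly changes the exact size of an uncorrected test.

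State in Section 15.3 whether the proportion test uses a continuity correction. Use one trigger in the synopsis and Section 15.5.1: the look takes place when 101 randomised, non-withdrawn patients have the 72-hour AKI outcome.

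The cost is one or two numbers, one sentence on the trigger in two places and a clause on the test. Sample size is unchanged, and power falls by less than one percentage point.
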